The use of intravesical gentamicin sulfate as a clinical strategy to prevent UTIs has been shown to be successful and safe in treating and suppressing recurrent UTIs in both adults and children (41-43). The administration of aminoglycosides (having primarily bactericidal activity against Gram-negative aerobes and facultative anaerobic bacilli) intravesically permits the use of high concentrations of antimicrobial solution targeting a local pharmacological effect while limiting systemic adverse effects such as nephrotoxicity, or impacting gastrointestinal flora. This approach helps prevent the development

of antimicrobial resistance. From the various aminoglycosides, gentamicin remains the best studied of these agents for bladder washout use and is the only intravesical treatment that has been shown to be safe and effective in both the prevention and treatment of UTIs (44, 45).

II. General Experimental Design

A. Objectives: The purpose of this feasibility study is to address the prevalence of chronic, recurrent urinary tract infections in adults living with a chronic, severe, spinal cord injury (SCI). We propose to determine if daily gentamicin bladder instillations reduce the rate of symptomatic UTIs as well as the use of oral and intravenous antibiotics in adults with chronic SCI who have recurrent UTIs. This study will test the efficacy of intravesical gentamicin delivery and provide insights into the mechanisms that underlie the benefits of this local pharmacological effect for translation into the clinic.

Overall Hypothesis: The use of a daily gentamicin instillation treatment will significantly decrease the incidence of catheter-associated complications, such as chronic symptomatic urinary tract infections as well as improve urological outcomes, thus greatly enhancing the quality of life for individuals with bladder dysfunction.

Specific Aim 1: To assess the effects of gentamicin bladder instillation (saline instillation and no instillation will serve as controls) on:1) bacteriuria (number and species, antimicrobial resistant bacteria, urinary leukocytes, and urinary pH), 2) risk factors for developing UTI (over-distention of the bladder, high-pressure voiding, large post-void residuals, detrusor sphincter dyssynergia, presence of stones, and signs of hydronephrosis resulting from vesico-ureteral reflux), and 3) individual tolerability (blood pressure outcomes).

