1. Blinding Plan: This is a double-blind study whereby the investigators, research assistants, research nurse and participants will be blinded as to the drug treatment designation. Once participants have been assessed for eligibility and enrolled in the study, they will be randomized into 1 of 3 different groups. Participants randomized to either group I or II will be blinded to the intervention fantibiotic instillation in group I or placebo (saline alone) in group II]. Gentamicin sulfate will be prescribed for the research participants by the study physician or nurse practitioner and instilled under the direction of the research nurse. Thus, the participants in groups I and II will not be able to discern their assigned treatment. To ensure the double-blind, only the study physician or nurse practitioner as well as the pharmacy, all of whom are not associated with the data collection or data analysis, will be un-blinded. Note, the research nurse assisting participants with the instillation will be blinded. All participants will be identified by number and the instillation solutions (gentamicin or placebo) will be numbered with the pharmacy having access to the code specifying which instillations are active and which are placebo for each participant. The investigators and direct research team members will not be permitted to have knowledge of the group assignments. In the case of a drug related adverse event, the study physicians will evaluate the event and prescribe treatment that will minimize or completely resolve the event if minor or moderate in severity and it does not interfere with activities of daily living or quality of life (as determined by the participant). Should it be determined that the event has gotten worse, or if the participant can no longer tolerate the event, the study drug will be discontinued, and the participant will be terminated from study participation. There are no expected reasons to unmask the study treatment. The study physician or nurse practitioner will decide if the blind is to be broken or not. The blind will not "routinely" be broken when a serious adverse event (SAE) occurs. If an SAE is probably or definitely drug-related, the drug/placebo intervention will be stopped, and the participant treated appropriately. Emergency drug code envelopes will be created by the pharmacy at the study site. These will be labeled by participant randomization number and contain information, which will un-blind the treatment of the individual subject. These envelopes are to be used only in extreme emergencies, such as when an emergency situation exists in which the participant's treatment would be affected by knowledge of his drug therapy, and there is no time to contact the Medical Monitor. Note, that at the end of the study, participants will be un-blinded to the intervention designation by the study physician or nurse practitioner. If a participant was randomized to the no instillation group, however, he/she may re-enroll into the study and directly receive the gentamicin intervention and are not required to wait until the end of study, as all parties are un-blinded and aware of the treatment (standard of care) in this instance. All data from participants re-enrolling into the gentamicin-only group will be kept separate from those who are enrolled in the main study who are blinded.

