
The following participant withdrawal criteria may be implemented in determining when and how to withdraw participants from the trial/investigational product treatment.

Drug Discontinuation Criteria:

The subject's participation may be terminated for safety precautions based on any of the following by the study investigator. 1) Drug-related severe adverse event; 2) UTI requiring intravenous antibiotics; 3) Diagnosis of systemic absorption; 4) Diagnosis of nephrotoxicity; 5) Diagnosis of ototoxicity; 6) Diagnosis of renal failure

Temporary Discontinuation Criteria:

Situations of temporary discontinuation of study drug followed by subsequent resumption of study drug are: 1) Resolution of an adverse event, especially in cases where it is determined that the study drug was unlikely to have caused the event. 2) Resolution of a symptomatic UTI.

Withdrawal from Study:

A participant may withdraw from study participation at any time. Whatever data has been collected at the time of study termination will be evaluated by the PI for use in the final study database. If a participant is terminated from the study, the investigator will have the option to recruit an additional participant. Of withdraw from the study was due to an adverse event, participants will be followed until complete resolution of the adverse event that was possibly or definitely drug-related.

2. Statistical Plan: Data will first be summarized. We will use means with associated standard deviation, median with associated interquartile range and full range (min-max) to summarize continuous variables. Categorical variables will be summarized with frequency count and standard deviation. We will perform 2 types of analyses: pre-post differences within each group and between group comparisons of the differences. To evaluate the pre-post changes in each group, we will use paired t-test. To compare the changes between the 3 groups, we will use ANOVA test. If the ANOVA test yields significant results, we will perform follow-up 2 by 2 group comparisons using 2-sample t-tests. If the underlying assumptions of these tests are not satisfied, we will use the non-parametric equivalent tests instead.

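### After permanent termination no UTI or antibiotic outcomes are planned, so data loss can depend on outcome and on arm

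*Combined protocol and SAP*

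**What the plan says.** - **II.B.1 Blinding Plan, main paragraph.** When a drug-related event has worsened or can no longer be tolerated, "the study drug will be discontinued, and the participant will be terminated from study participation". This is mandatory. A later sentence, on a serious adverse event judged probably or definitely due to the drug, stops the intervention and does not mention termination.
- **Drug Discontinuation Criteria.** The heading concerns the drug, but the action concerns the person: "The subject's participation may be terminated for safety precautions based on any of the following by the study investigator". Six grounds follow, among them "2) UTI requiring intravenous antibiotics".
- **Temporary Discontinuation Criteria.** The drug may be paused and resumed once an adverse event or a symptomatic UTI has resolved. The participant stays in.
- **Withdrawal from Study.** On data: "Whatever data has been collected at the time of study termination will be evaluated by the PI for use in the final study database". On numbers: "If a participant is terminated from the study, the investigator will have the option to recruit an additional participant". After withdrawal for an adverse event, "participants will be followed until complete resolution of the adverse event that was possibly or definitely drug-related". No other follow-up is described.
- **II.A Objectives.** The question is whether daily gentamicin instillations "reduce the rate of symptomatic UTIs as well as the use of oral and intravenous antibiotics".
- **II.B.2 Statistical Plan.** Pre-post changes are compared between the three groups by ANOVA and then t-tests. No analysis population, missing-data method or dropout allowance is given.

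**The concern.** Stopping a treatment and leaving a trial are different events. Where the plan merges them, UTIs and antibiotic courses after that day are not planned to be recorded, and no later analysis rule can recover them. People who stop permanently are unlikely to be a random subset. One ground for ending participation is itself a bad efficacy outcome. The mandatory rule is triggered by a drug-related event, and the no-instillation arm has no study drug. With 12 per arm, a few such losses can move a group mean by an amount that matters, and the data needed to check for it would not exist.

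**Working it through.** **1. Which stops end outcome collection**

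| Situation | Where | Participation | UTI and antibiotic data afterwards |
|---|---|---|---|
| Drug-related event worsens or is intolerable | II.B.1 | Ends (mandatory) | None planned |
| Any of six listed grounds | Drug Discontinuation Criteria | May end (discretion) | None planned if ended |
| Serious event probably or definitely due to drug | II.B.1 | Not stated | Not stated |
| Pause, then resumption | Temporary Discontinuation Criteria | Continues | Continues |

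A drug-related severe event is also the first of the six discretionary grounds. Drug-related events are therefore handled under three wordings with different consequences for participation, and these need to be reconciled.

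**2. The plan's own power figure**

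Inputs (II.B.2): 12 against 12, difference 2, SDs 1.7 and 0, two-sided 0.05, unequal-variance t-test. The standard error is √(1.7²/12 + 0) = 0.491, the noncentrality 2/0.491 = 4.08, and the Welch df 11. Power is 95.9%, against 96% stated. The arithmetic is sound, but the powered number equals the enrolled number, so nothing is allowed for losses.

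**3. Expected drop on the 80-day scale**

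II.B.2 expects a drop of 2 UTIs in 6 months: 2 × 80/182.5 = 0.88 per 80 days.

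**4. Size of the undercount**

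Assumptions, since the documents give no stopping rate: 2 of 12 stop halfway, their UTI rate is twice the arm rate *r* (per 80 days), and raw counts are analysed with unobserved time contributing nothing.

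Undercount in the arm mean = (2/12) × (2 × *r* × 0.5) = *r*/6.

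| Arm rate *r* | Source | Undercount | Share of 0.88 |
|---|---|---|---|
| 1.3 | Assumption: about 3 per 6 months (3 × 80/182.5) | 0.22 | 25% |
| 0.88 | Entry minimum, 2 per 6 months (III) | 0.15 | 17% |
| 0.66 | Entry minimum, 3 per year: 3 × 80/365 | 0.11 | 12.5% |
| 0.55 | 2.5 per year (I.B): 2.5 × 80/365 | 0.09 | 10% |
| 0.42 | Gentamicin arm on treatment if baseline is 1.3: 1.3 − 0.88 | 0.07 | 8% |

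If each participant's count is instead divided by that participant's own days observed and then averaged, and each rate is constant over time, this loss disappears.

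**5. When an undercount becomes a between-arm bias**

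A simulation (40,000 runs, no true difference, both arms SD 1.7 by assumption, Welch test) took the case in which stoppers are dropped and each arm is filled up to 12 completers. The plan does not specify that analysis; it serves only to show the conditions.

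- 20% stop in one arm only, unrelated to outcome: no shift, type I error 5.0%.
- 20% stop in one arm only, correlation with outcome 0.5: spurious shift 0.30 UTIs, error 6.9%. At correlation 1, an upper bound: 0.59 UTIs, 13.9%.
- 20% stop in both arms, correlation 0.5: no shift, error 5.0%.

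Both conditions are needed: stopping related to outcome, and stopping that differs by arm.

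**6. Direction**

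Lost counts in the gentamicin arm, for example after drug-related events, favour gentamicin. Lost counts in the control arms, for example after UTIs treated intravenously, work against it. The sign cannot be fixed in advance.

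**The case against.** The case on the other side is substantial.

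- **A reader might infer that every stop ends participation.** The text does not say so. Termination is mandatory in one situation only, the six criteria are discretionary, and pauses are allowed. The urine-culture section leaves continuing instillation or clamping during systemic antibiotics to the clinician. III.E.3.a returns a participant with a procedure-related serious event to the laboratory for at least a week and does not remove that person.
- **A reader might infer that the arms will fill with completers.** That depends on how partial data are used, and the plan says they will be evaluated for use. Recruiting someone further is optional, and the text calls that person additional, not a replacement.
- **A reader might infer that newcomers escape randomisation.** II.B.1 randomises everyone who is enrolled. The one exception is re-enrolment from the no-instillation group, whose data are kept apart. What is missing is an explicit statement for this case.
- **The top of the range is soft.** The 1.3 UTIs per 80 days is not in the documents. II.A speaks of a rate, although Hypothesis 1.1 speaks of episodes, so the count-based loss may not arise.
- **The study calls itself a feasibility study,** and end-of-study urodynamics carries listed risks, so full assessment of everyone who stops cannot simply be required.

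These points narrow the concern. They do not answer its core: no UTI or antibiotic follow-up is planned after permanent termination. A per-day rate removes the loss only if the rate after stopping equals the rate before, which could not be checked without later data.

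**Conclusion.** The concern holds in a limited form. For participants permanently terminated, efficacy outcomes are not planned to be collected; adverse events are followed to resolution and earlier data may be used. One ground for termination belongs to the efficacy question, and the mandatory rule turns on a drug that one arm does not receive, so outcome-related and unequal loss is plausible. It is not demonstrated, and its direction is open.

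The 8% to 25% range is an illustration. It rests on the assumed 2 of 12 stopping, halfway, at twice the arm rate, with raw counts analysed; the entry minimums give 12.5% to 17%. The documents do not support saying that gentamicin's benefit will be inflated or that randomisation is abandoned. This is a cheap improvement worth making, not a fatal flaw.

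**What to change.** Amend II.B.1 and the discontinuation and withdrawal text that follows it:

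1. Reconcile the mandatory rule, the discretionary list and the serious-event sentence, so that each says what happens to the intervention and what happens to follow-up.
2. Separate stopping the intervention from leaving outcome follow-up. Unless consent is withdrawn, keep recording symptomatic UTIs and antibiotic courses, by phone or from records, to the planned end of the 80-day period.
3. Hold any end-of-study assessment, including urodynamics, only where the study clinician judges it appropriate.
4. In II.B.2, analyse all participants as randomised.
5. State that any additional participant takes the next random assignment and does not displace the one who stopped.

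The clinical grounds for stopping stay as they are, and so does the investigator's power to act on them for safety. The cost is a small amendment and a few follow-up contacts.

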sessions will be performed in the laboratory. The time frame to retain the instillation treatment in the bladder will be incrementally increased by 15 minute intervals in the laboratory over the course of 3 - 4 weeks. Instillation retention times may begin for 30 minutes. Once 3 consecutive days of stable blood pressure values without autonomic dysreflexia are demonstrated during that time frame, the time will be increased to 45 minutes and the same process will continue by 15 minute intervals, up to 2 hours, as long as blood pressure remains stable throughout the instillation retention time frame. The instillation retention time frame will not be increased if the participant experiences autonomic dysreflexia and thus, an optimal time frame in which his/her blood pressure remains stable during the intervention will be established. Once 3 consecutive stable days are achieved with the same instillation parameters and the participant has demonstrated self-sufficient use of the instillation procedure, he/she will be sent home for one day to perform the twice daily instillations at home. For home instillations, the participant will be instructed and provided with written instructions indicating that the solution is to be stored in the refrigerator no more than 10 days and stored at room temperature for no more than 48 hours. The participant will return to the laboratory the following day for instillation with blood pressure monitoring. Provided blood pressure parameters remain stable, the participant will be allowed to complete the intervention at home for 3 days prior to returning to the laboratory for instillation and blood pressure monitoring. If blood pressure parameters remain stable, the participant will be able to begin the home intervention program of 6 days a week and 1 day in the lab. Participants will be instructed to monitor blood pressure for at least 15 minutes.

2. Saline Instillation

A 50ml syringe containing saline will be connected to the end of the catheter and slowly infused over 1-2 minutes after drainage of urine is complete. The saline will remain in the participant's bladder for at least 30 minutes (unless the participant is experiencing autonomic dysreflexia, and in that case, immediately drained) with the goal of attaining 2 hours. Note that participants will follow the same instillation training paradigm as mentioned above, including the incremental progression of instillation retention time with stable blood pressure values.

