An assessment of metabolic parameters (glucose, calcium, albumin, total protein, blood urea nitrogen, creatinine, alkaline phosphatase, alanine amino transferase, aspartate amino transferase, bilirubin, and other electrolytes), inflammatory markers (C-reactive protein, erythrocyte sedimentation rate, procalcitonin), and complete blood count (includes white blood cells, red blood cells, hematocrit, and platelets) will be performed. A trained technician will insert a butterfly catheter into an antecubital vein to allow the collection of blood. Blood samples will be sent to the Outpatient Care Center, Jewish Hospital for testing.

6. Urodynamics

The participant will be asked to refrain from taking any bladder medications 24-hours prior to Urodynamics. For the urodynamic study (necessary to determine bladder function/voiding pressures/degree of detrusor sphincter dyssynergia (53, 54)), a complex cystometrogram (to evaluate the filling phase of the bladder) with a pressure flow study and simultaneous abdominal pressures and flow rate (to evaluate the voiding phase of the bladder) will be performed. The cystometry evaluation is accomplished using standard procedures (55-57), measuring bladder pressure during filling, possible uninhibited bladder contractions and maximum cystometric capacity, with determination of the leak point pressure and post-void residual volume when voiding is possible at the end of the study when a second uroflow can be obtained. A 12 French straight catheter will be used to empty the bladder completely for a urine sample to be collected and assessed for the presence of blood, urobilinogen, glucose, ketones, bilirubin, protein, nitrites, leukocytes, pH, and specific gravity using DiaScreen reagent strips for urinalysis. The collected urine sample may also be sent out for culture. Then a 7 French urodynamic catheter will be placed in the bladder to fill the bladder as well as to measure and record intra-vesical pressure. Another catheter with a balloon will be placed in the rectum to record the intra-abdominal pressure. Detrusor pressures will be calculated by subtracting the intra-abdominal pressure from the intra-vesical pressure.

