University of Louisville Hospital and Frazier Rehab Institute evaluates approximately 300 chronic SCI outpatients each year. We also have a database of over 5,000 people with SCI who have expressed interest in participating in our research programs. We will select individuals to assure that there is a minimum of 25% women to adequately represent the percentage in the SCI population.

All SCI research participants, irrespective of gender, will be selected based on the following:

Inclusion Criteria

- At least 18 years of age;
- Non-progressive spinal cord injury;
- Stable medical condition;
- Bladder dysfunction as a result of spinal cord injury
- History of recurrent UTIs (defined as 3 or more within the past year or 2 or more within the past 6 months).

Exclusion Criteria

- Signs or symptoms of serious UTI that requires the use of systemic antibiotics;
- Use of any urine-acidifying agent, bladder irrigant, or systemic antibiotic within the previous 2 weeks;
- Participants colonized with gentamicin-resistant bacteria on baseline urine culture or a gentamicin allergy/sensitivity;
- Participants with known hearing loss and/or renal disease;
- Pregnant at the time of enrollment or planning to become pregnant during the time course of the study.

A. Screening and Enrollment

Potential research participants will be identified by our research database (UofL IRB 06.0647) and contacted by research staff prioritized by the initial date they entered the database and provided with general information regarding the research study. If the individual is interested in learning more about the study, the clinical coordinator will set up an info session via teleconference or a meeting at Frazier Rehab Institute. The designated project leader and clinical coordinator will attend the info session and the project leaders (Drs. [name] and [name]) will describe the project including the time commitment, the general design of the study, the interventions and the randomization process. Specific questions from the potential research participant will be answered.

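### Ototoxicity and systemic absorption are stopping grounds, but after screening no described assessment asks about hearing, tinnitus or balance or measures a gentamicin level; short weekly questions at existing visits would narrow the gap

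*Combined protocol and SAP*

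**What the plan says.** **Stopping.** Under Drug Discontinuation Criteria (Section II.B.1), participation "may be terminated for safety precautions based on any of the following by the study investigator". The list includes "3) Diagnosis of systemic absorption; 4) Diagnosis of nephrotoxicity; 5) Diagnosis of ototoxicity; 6) Diagnosis of renal failure". It gives no test, threshold or schedule for these diagnoses. The Blinding Plan in the same section is firmer. A drug-related event that worsens or can no longer be tolerated ends study drug and participation, and a serious adverse event judged probably or definitely drug-related stops the intervention.

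**Screening.** The exclusion criteria in Section III list "Participants with known hearing loss and/or renal disease". A nurse practitioner takes a history and examines the participant (III.A), and the participant attests to eligibility on a checklist (III.B).

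**On treatment.** The Blood Draw section includes "total protein, blood urea nitrogen, creatinine, alkaline phosphatase", together with inflammatory markers and a blood count. Figure 2 schedules laboratory tests, urodynamics, ultrasound and intake forms at screening, midpoint and post-intervention. The two described data sets cover UTI signs, bladder emptying, incontinence and medication. After start-up, participants "begin the home intervention program of 6 days a week and 1 day in the lab".

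**Risk text.** Section III.D.1 lists ringing, hearing loss and dizziness under intravenous gentamicin, and says that route is not used here. The list for bladder instillation puts uptake of the drug from the bladder in the rare band (0-10%) and has no hearing or balance item.

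**The concern.** A stopping ground protects a participant only if something in the plan can bring it to light. Renal toxicity has such a step in the scheduled creatinine and urea nitrogen. Ototoxicity and systemic absorption have none described once treatment begins.

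What is at stake is the care of individual participants, not a trial-level safety claim. A participant with early ringing or unsteadiness keeps dosing twice a day until they mention it, someone notices, or a clinician orders a test for another reason. Prompting to mention it is weak: the risk text links these symptoms to a route not used in the study, and the home-phase instruction to call (III.E.3) names only complications of bladder distention. The people exposed may also exceed the 12 randomised to gentamicin. A no-instillation participant "he/she may re-enroll into the study and directly receive the gentamicin intervention", and after a termination "the investigator will have the option to recruit an additional participant".

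**Working it through.** **1. Exposure (the plan's own figure first).** 480 mg/L x 0.060 L = 28.8 mg per instillation, which reproduces Figure 2. Twice daily this is 28.8 x 2 = 57.6 mg. Over 80 days x 2 = 160 instillations, 28.8 x 160 = 4,608 mg, about 4.6 g instilled (not absorbed). Figure 2 shows two blocks of 80 instillations, so midpoint falls at 80 / 2 = day 40.

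**2. Where a detection step could sit.**

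| Place in the plan | Hearing, tinnitus or balance | Gentamicin level |
|---|---|---|
| Eligibility, history, checklist (III, III.A, III.B) | Known hearing loss, before treatment only | No |
| Aim 1 tolerability (II.A) | No; blood pressure only | No |
| Blood Draw; Figure 2 laboratory tests | No | No; urea nitrogen and creatinine cover the renal grounds |
| Described data sets | No | No |
| Intake forms (Figure 2) | Content not described | Not applicable |
| Monitoring at assessments (III.E.2) | Generic discomfort and adverse reactions | No |
| Event log, weekly report to study physician (III.E.4) | Only what the team learns of | No |

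A midpoint rise in creatinine could prompt a drug level. Absorption with normal creatinine and no symptoms would not be found by any described step.

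**3. Time away from the laboratory.** Start-up is about 1 to 2 weeks in II.B and 3 to 4 weeks in the instillation section, so I take 1 to 4 weeks (assumption). The step-down is 1 home + 1 laboratory + 3 home + 1 laboratory = 6 days. The home programme then covers 80 - 28 - 6 = 46 to 80 - 7 - 6 = 67 of the 80 days.

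**4. When questions must start.** If they were asked only on the weekly laboratory days of the home programme, the first would fall between day 7 + 6 + 7 = 20 and day 28 + 6 + 7 = 41. In the slow case the midpoint, at day 40, comes first, after 80 of 160 instillations. Participants attend the laboratory throughout start-up and twice in the step-down, so weekly questions can begin in week 1 without a new visit.

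**5. Workload.** 80 / 7 = 11.4, so 11 complete weeks. Adding screening, midpoint and post-intervention gives 11 + 3 = 14 contacts per participant (13 if one weekly contact coincides with midpoint). For the 24 participants in the gentamicin and saline arms, 24 x 14 = 336 question sets. If all 12 no-instillation participants re-enrol on the same schedule (assumption), 36 x 14 = 504. Replacements would add to both. The on-treatment gap becomes about 7 days, or 7 x 2 = 14 instillations.

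**6. What one drug level each in 12 gentamicin participants could show.** The chance of at least one positive is 1 - (1 - p)^12: 72% if p = 10% (top of the plan's rare band), 46% at 5%, 11% at 1%. These assume that the single level catches every true case. Finding 0 of 12 leaves a one-sided 95% upper bound of 1 - 0.05^(1/12) = 22.1%.

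**The case against.** The sponsor has a fair case. Section I argues that delivery into the bladder limits systemic effects and cites experience that it is safe. The risk text ties ototoxicity to intravenous use and higher doses. Known hearing loss and renal disease are excluded, and renal chemistry is scheduled. Staff watch participants at every assessment, logged events reach the study physician weekly, and serious events go to the Medical Monitor in real time. Participants do read about ringing and dizziness. The intake forms may already hold such items, and the consent pages are not available to check.

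Most of this stands as a reason not to demand audiometry or routine drug levels. It does not supply an on-treatment question for a ground that the plan itself lists.

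A reader might infer more than the documents support:

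- **That the plan ignores hearing.** It does not; known hearing loss is dealt with before enrolment.
- **That stopping is purely discretionary.** The Blinding Plan makes it mandatory for worsening, intolerable or serious drug-related events. What is missing is the step by which a milder event is recognised.
- **That none of the listed toxicities can be detected.** The renal grounds are covered.
- **That events at home go unreported.** The same-day limit in III.E.4 sits under a heading on events unrelated to the study, and III.E.5 requires all adverse events to be reported.
- **That a serum level is required.** A level would need a stated sampling time, an action threshold and blinding safeguards. Figure 2 does not say whether dosing continues in the 5-day midpoint window, and step 6 shows how little one level per participant could establish for the trial.

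**Conclusion.** The point holds in a limited form. Between screening and the end of treatment, no described assessment asks about hearing, tinnitus or balance or measures a gentamicin level, although ototoxicity and systemic absorption are listed stopping grounds. Early ototoxicity is left to volunteered reports and generic monitoring over up to 160 instillations. Those at risk are 12 participants, up to 12 + 12 = 24 if every no-instillation participant re-enrols, plus replacements.

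This is a cheap improvement to individual safety, not a defect in the efficacy analysis; sample size and power are unaffected. The conclusion rests on the described text. If the intake forms already contain these items, screening, midpoint and post-intervention are covered, and only the weekly questions and the call instruction remain to be added. The documents give no costs, so calling it cheap is a judgement based on using existing visits.

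**What to change.** **Questions.** Add a short fixed set on hearing, tinnitus and balance at:

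- screening, to give a baseline answer;
- at least once a week from the first laboratory start-up week;
- each weekly laboratory day of the home programme;
- midpoint and post-intervention.

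Ask everyone receiving instillations, in both blinded arms and among those re-enrolled to gentamicin. The blinded research nurse can ask them. Any new positive answer is evaluated by the study physician or nurse practitioner. The plan already limits unblinded access to "only the study physician or nurse practitioner as well as the pharmacy", so this adds no unblinded role.

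**Call instruction.** Extend the home-phase instruction in III.E.3 to new ringing, hearing change, dizziness or unsteadiness.

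**Cost.** A protocol amendment and a few minutes at each existing visit, about 336 question sets in the main study and up to 504 with full re-enrolment, before replacements. The questions will miss subclinical hearing loss and silent absorption.

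**Optional.** A midpoint serum gentamicin level could be considered separately. It should be added only with a fixed sampling time after an instillation, a stated action threshold, sampling in both blinded arms, and results kept from the blinded investigators.
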